Objectives:	
Primary Objective: To determine the efficacy of incentive spirometry to improve FEV1 in the preoperative surgical setting.
 
Secondary Objectives:
 
 1. To determine the efficacy of incentive spirometry to improve FVC and pulse oximetry in the preoperative surgical setting. 2. To determine the change in FEV1, FVC and pulse oximetry after surgery. 
Exploratory Objectives:
 
 1. To determine the daily number of times patients perform incentive spirometry in the preoperative and postoperative setting. 2. To determine whether standard incentive spirometers move throughout a patients' postoperative stay using accelerometers, as a proxy for how often patient uses the device. 3. To evaluate whether a digital IS device + text message based mobile health intervention will improve FEV1, FVC, and pulse oximetry compared to standard IS. 4. To evaluate the rate of pulmonary complications across the 3 preoperative groups.
Endpoints:	
Primary Endpoint: Change in FEV1 at day-of-surgery preoperative from baseline
 
Secondary Endpoints:
 
 1. Change in FVC and pulse oximetry at day-of-surgery preoperative from baseline 2. Change in FEV1, FVC and pulse oximetry at postoperative day 3 from day 1

	
Exploratory Endpoints:
 
 1. Daily frequency of digital IS use. 2. Movement data of standard IS with accelerometers (this is a proxy endpoint for IS use). 3. Difference in changes in FEV1, FVC, and pulse oximetry between randomized groups. 4. Postoperative complications defined by Modified Accordion Grading System (MAGS)
Study Population:	We plan to enroll 156 adult patients who are scheduled to undergo major abdominal surgery with an expected postoperative hospital stay of \geq 48 hours.
Phase:	N/A
Description of Sites / Facilities Enrolling:	The study will take place at Barnes Jewish Hospital system/Washington University School of Medicine.

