2.0 OBJECTIVES AND ENDPOINTS

Objectives	Endpoints	Justification for Endpoints
Primary		
To determine the efficacy of incentive spirometry to improve FEV1 in the preoperative surgical setting.	Change in FEV1 at day-of-surgery preoperative from baseline	

Secondary		

3. To determine the efficacy of incentive spirometry to improve FVC and pulse oximetry in the preoperative surgical setting.
 
4. To determine the change in FEV1, FVC and pulse oximetry after surgery.
	
1. Change in FVC and pulse oximetry at day-of-surgery preoperative from baseline
 
2. Change in FEV1, FVC and pulse oximetry at postoperative day 3 from day 1
	
Tertiary/Exploratory		

1. To determine the number of times patients perform incentive spirometry in the preoperative and postoperative setting.
 
2. To determine whether standard incentive spirometers move throughout a patients' postoperative stay using accelerometers, as a proxy for how often patient uses the device..
 
3. To evaluate whether a digital IS device + text message based mobile health intervention will improve FEV1, FVC, and pulse oximetry compared to standard IS.
 
4. To evaluate the rate of pulmonary complications across all 6 groups.
	
1. Daily frequency of IS use
 
2. Postoperative complications defined by Modified Accordion Grading System (MAGS)
	

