On the day of surgery, PFTs and pulse oximetry on room air will be recorded for all patients in the preoperative area. After surgery, all patients will receive a spirometer as is standard of care. On postoperative day 1, patients will be re-randomized. Those in the standard group will receive a standard spirometer for postoperative use, whereas patients in the digital group will obtain a digital spirometer (Spirobank G + ZEPHYRx®-enabled). All patients will receive instruction on how to perform spirometry and will be instructed to perform spirometry 10 times per hour, every hour while awake as is current practice for the department of surgery. The conventional spirometer will be equipped with an accelerometer that will allow the research team to determine whether the spirometer moves throughout the patients' postoperative stay (as a proxy for IS use) in the standard group. Compliance amongst the digital group will be determined using the ZEPHYRx® dashboard as described above. Just as in the preoperative period, the digital group will receive text reminders to perform spirometry if they do not perform spirometry in a 24-

hour period. PFTs and pulse oximetry on room air will be obtained on postoperative day 1 and postoperative day 3. The clinical inpatient team will be blinded to compliance data.

After obtaining final measurements on postoperative day 3, the study will conclude, and the spirometers will be collected. Postoperative outcomes data, including perioperative mortality postoperative complications, length of stay, and need for readmission, will be collected for all patients as per protocol for the Division of Hepatobiliary Surgery.

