9.3 Data Collection

FEV1, FVC, and pulse oximetry will be obtained for all patients at 4 different time points: (1) baseline measurement at the time of enrollment; (2) preoperatively on the day of surgery; (3) immediate postoperative period 24 hrs after surgery; and (4) delayed postoperative period on postoperative day 3. The digital spirometer couples with a HIPAA-compliant mobile app which stores data and shares it with the research team via a HIPAA-compliant dashboard. These data will be used to assess compliance with the intervention for the digital group both in the preoperative and postoperative period. Sustained accelerometer movement data will be used as a surrogate for frequency of use and will be

used to assess compliance with the intervention for the standard group in the postoperative period.

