9.4 Endpoints

The primary endpoint is FEV1 change at day-of-surgery preoperative from baseline. The secondary endpoints include FVC and pulse oximetry change at day-of-surgery preoperative from baseline, change in FEV1, FVC and pulse oximetry at preoperative day 3 from day 1. Exploratory Endpoints are daily frequency of IS use and postoperative complications defined my Modified Accordion Grading System (MAGS).³⁹

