9.6 Data Analysis

The analysis will be intent-to-treat approach. The FEV1, FVC and pulse oximetry changes at day-of-surgery preoperative from baseline will be compared across three groups using ANOVA or Kruskal-Wallis test, as appropriate. The linear regression model will be considered to adjust for the other interested variables including age, sex, smoking status, BMI, ASA, and malignancy. The same analysis method will be conducted for FEV1, FVC and pulse oximetry changes at preoperative day 3 from day 1. The frequency of use, defined as the daily number of times patients perform incentive spirometry, will be compared across all groups in the postoperative setting using ANOVA or Kruskal-Wallis test, as appropriate. For postoperative complications, Chi-square test will be used to test the differences between six groups. The univariate logistic regression model will estimate the odds ratio of postoperative complication. Multivariate analysis through stepwise selection will be considered to examine the relationship between binary outcome and independent predictors, where a significance level of 0.3 is required to allow a predictor into the model, and a significance level of 0.35 is required for a predictor to stay in the model. All analyses will be conducted using SAS (SAS Institute, Cary, NC) at the two-sided 5% significance level.

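### Section 9.6 compares postoperative spirometer use as one count across all groups, but digital use comes from a dashboard and standard use from an accelerometer proxy, so digital-versus-standard contrasts are confounded with the instrument

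*Combined protocol and SAP*

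**What the plan says.** **Analysis.** Section 9.6 defines one use variable and says that the "daily number of times patients perform incentive spirometry, will be compared across all groups in the postoperative setting". It does not define *all groups*. Later in the same section, for complications, a "Chi-square test will be used to test the differences between six groups".

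**Data sources.** Sections 5.0 and 9.3 take digital-arm use from the dashboard, before and after surgery. After surgery the standard spirometer is "equipped with an accelerometer that will allow the research team to determine whether the spirometer moves throughout" the stay. Section 9.3 adds: "Sustained accelerometer movement data will be used as a surrogate for frequency of use", and confines this to the postoperative period.

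**Endpoints.** The synopsis lists two: "Daily frequency of digital IS use" and "Movement data of standard IS with accelerometers (this is a proxy endpoint for IS use". The endpoint column of Section 2.0 has only "Daily frequency of IS use", although its objectives column still carries accelerometer movement as a separate item. Section 9.4 reads: "Exploratory Endpoints are daily frequency of IS use and postoperative complications".

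**Hypotheses.** The synopsis and Section 1.2 expect spirometry to improve lung function after controlling for compliance, and expect the digital device with text messages to improve postoperative compliance. The regression in Section 9.6 names age, sex, smoking, BMI, ASA and malignancy, but not compliance. The use objective covers both periods in the synopsis and Section 2.0, and only the postoperative period in Section 9.1.

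**The concern.** After surgery the measuring instrument coincides exactly with the randomised device. An app that logs spirometry and a sensor that registers movement can give different daily totals for the same behaviour. A device may be moved without being used, and one session may register as several movements or as none. With no threshold for sustained movement and no conversion to a count, the standard-arm figure is not known to be on the scale that Section 9.6 assumes.

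At stake is the hypothesis that the digital device improves postoperative compliance, since this is the only planned comparison of use. A significant result could be a sensor difference, and a null result could hide a real one. The protocol also faults earlier studies for not measuring and adjusting for compliance, so readers will look to this result.

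A related gap lies before surgery: no source of use data is named for the standard arm, although the objective asks for preoperative use.

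**Working it through.** **1. The plan's own figure.** The only computed design figure is the power for FEV1: 49 per group, difference 0.4 L, SD 0.6, two-sided alpha 0.017. The noncentral t gives 80.62% against the stated 80.6%, and 49/0.95 = 51.6 rounds up to 52 per group, 156 in all. It reproduces and does not bear on this point.

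**2. What can be identified.** Let μD and μS be true mean daily use in the two postoperative arms, and b the mean difference between what the dashboard and the accelerometer record for the same use. The recorded difference estimates

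(μD − μS) + b.

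Every digital patient has one instrument and every standard patient the other, so these data cannot separate the two terms. Among former preoperative groups within one device, b does not enter. Among former groups pooled over device, each group carries about the same share of each instrument, so b cancels approximately. Exact cancellation needs balanced re-randomisation; Section 9.2 mentions no stratification by former group.

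**3. Readings of *all groups*.**

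| Reading | Confounded with instrument? |
|---|---|
| Two postoperative arms | Yes |
| Six groups (3 preoperative × 2 postoperative) | 3 × 3 = 9 of 6 × 5/2 = 15 pairs; the other 3 + 3 = 6 are not |
| Three preoperative groups pooled over device | No, given balance |

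**4. Illustration only.** The documents give no sensor offset, direction, or coefficient of variation (CV) of use. Assume equal true use, a 20% offset, CV 0.5 to 1.0, 1:1 re-randomisation and 5% loss (156 × 0.95 = 148.2, about 148). The 5% is borrowed from Section 9.5, where it applies to the primary outcome.

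- Constant-SD shift: d = 0.20/CV, noncentral F with λ = 148(d/2)². For CV 0.5, d = 0.40 and λ = 5.92. The chance of p < 0.05 is 68% (CV 0.5) to 23% (CV 1.0) for two groups, and 41% to 12% for six.
- Sensor that scales counts instead (simulation, gamma-distributed use, two-group t-test, CV 0.5): about 76% if it reads 20% low and 59% if it reads 20% high.
- Three preoperative groups pooled over device, sensor reading 20% low (cells of 25, 25 and 24 per device): about 4% to 5%.
- Three former groups within the standard device: about 5%.

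The first two lines move with assumptions that the documents cannot settle. The last two confirm which comparisons are safe.

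**5. Coverage of use data.**

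| | Before surgery | After surgery |
|---|---|---|
| Digital | Dashboard | Dashboard |
| Standard | None named | Accelerometer proxy |

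Section 5.0 gives the preoperative standard arm a conventional spirometer, and the form schedule in Section 7.0 lists no use log. Planned spirometry patients before surgery: 52 + 52 = 104, of whom 52 have no named source.

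**The case against.** **The wording may mean the three preoperative groups.** Section 9.6 opens with a three-group comparison, and Section 9.1 names the three preoperative groups for complications. On that reading the instrument is roughly balanced and the test is sound. This stands, and it limits the point to contrasts between the postoperative devices. It does not remove the point: the phrase is undefined, the section elsewhere uses six groups, and on the three-group reading the postoperative-compliance hypothesis would have no test.

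**The proxy is disclosed.** It is, in the synopsis and in Section 9.3, and Section 2.0 keeps movement as its own objective. Disclosure does not put movement on the scale of a count, and Sections 9.4 and 9.6 drop the label.

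**The covariate list is open-ended.** Compliance adjustment is thus unspecified rather than ruled out. This stands. The missing model is mainly missing detail, and compliance, as a post-randomisation variable, should not simply be added as a covariate. The missing preoperative source for standard IS is more than detail.

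**The endpoint is exploratory.** True, and the urgency is set accordingly.

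A reader might go further and infer that every use comparison is invalid, or that a false positive has a known high probability. The documents support neither: comparisons among former preoperative groups are unaffected, and every input to the probabilities above is assumed.

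**Conclusion.** The concern holds for contrasts between the re-randomised postoperative digital and standard arms: the two-arm comparison, or the 9 cross-device pairs of six. There, a difference in recorded use cannot be told apart from a difference between instruments. This conclusion is structural and needs no numerical assumption beyond the two data sources that the protocol describes. The size and sign of the bias cannot be derived from the documents.

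Two smaller points go with it. Preoperative use cannot be determined for the standard arm from any named source, and the planned intent-to-treat analysis does not test the hypothesis as phrased, with control for compliance. It would be wrong to infer that the primary result is in doubt: the intent-to-treat FEV1 comparison uses no compliance data, and its sample size is unaffected. The changes should be made before analysis, but they do not threaten the trial's main conclusion.

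**What to change.** 1. In the endpoint column of Section 2.0, and in Sections 9.4 and 9.6, restore the synopsis's two endpoints. Define the counting unit for digital use and the threshold for sustained movement. Possible text for 9.6: *Digital IS frequency and standard-device movement will each be summarised by day within the corresponding postoperative arm. Former preoperative groups may be compared within an arm. Counts will not be tested between devices.* State which groups are meant wherever the section now says all groups. If a between-device contrast is kept, use one coarse unit that both streams yield, such as the share of named clock-hours with any recorded use or sustained movement (time-stamping assumed). Label it proxy-based and not evidence of a compliance difference.
2. Reword the postoperative-compliance hypothesis in the synopsis and Section 1.2 to match, as descriptive or proxy-based. Otherwise item 1 leaves it without a test.
3. Limit the preoperative-use objective to the digital arm, and reconcile the synopsis, Section 2.0 and Section 9.1.
4. State that the planned analysis is intent-to-treat and does not test a compliance-controlled effect, or drop that phrase from the hypothesis.

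**Cost.** One amendment with IRB review; no new devices, patients or visits. The trial gives up its between-arm postoperative compliance claim, or labels it proxy-based. Within-device comparisons rest on about 148/2 = 74 patients, or about 25 per former group, under the assumed 1:1 re-randomisation and 5% loss. The 95% half-width for a pairwise difference is then about 1.96 × √(2/25) = 0.55 SD, which is imprecise. Keeping the original aims would need a common sensor or a validation subset after surgery, and a use log or sensor for standard IS before it. Those require new data collection.

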Description of Study Intervention:	Patients will be randomized into 3 groups: (1) control group with no IS, (2) standard IS, and (3) digital IS + text message. Groups 2 and 3 will be instructed to perform spirometry every day for at least 7 days prior to surgery. FEV1, FVC, and pulse oximetry will be obtained for all patients at 4 different time points: (1) baseline measurement at the time of enrollment, (2) preoperatively on the day of surgery, (3) immediate postoperative period 24 hours after surgery, and (4) delayed postoperative period on postoperative day 3. After surgery, patients are re-randomized to conventional spirometry (which is standard of care) or digital spirometry. The digital spirometer couples with a HIPAA-compliant mobile app which stores data and shares it with the research team via the HIPAA-compliant dashboard. These data will be used to assess compliance with the intervention for the digital group both in the preoperative and postoperative period. Sustained accelerometer movement data will be used as a surrogate for frequency of use and will be used to assess compliance with the intervention for the standard group in the postoperative period.
Study Duration:	Approximately 1000 major abdominal surgeries take place at our institution yearly. The rate-limiting step for enrollment is going to be the digital IS devices, which we plan to re-use. Purchasing 20-30 devices for 150 patients, we anticipate completing accrual in 12 months. (Note that all patients receive an individualized spirometry mouthpiece; only the digital device that does not come into contact with patient is re-used.) We anticipate data analysis will be completed 6 months following closure to accrual.
Participant Duration:	Approximately 1 month

SCHEMA

SCHEDULE OF ACTIVITIES

	Baseline/Enrollment	Pre-operative Days 1-7	Day of surgery	Post-operative Day 1	Post-operative Day 3
Consent¹	X				
Randomization²	X				
Re-randomization³				X	
Spirometry intervention		X ⁵		X	X
FEV1, FVC, pulse oximetry	X		X ⁴	X	X
Assess for AE/Complications	X	X	X	X	X

Notes:

1. Consent should take place not less than 8 days prior to surgery.
2. Patients will be randomized into three groups: (1) control group with no IS, (2) standard IS, and (3) digital IS + text message.
3. Following surgery, patients will be re-randomized into two groups: (1) standard IS, and (2) digital IS + text message.
4. Measurement of PFTs and pulse oximetry should be obtained prior to surgery on the day of surgery.

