9.0 STATISTICAL CONSIDERATIONS

9.1 Study Design

This is a prospective, single-center, randomized trial. The enrolled patients will be randomized 1:1:1 to one of three groups: control, standard IS, and digital IS + text message. They will have baseline measurement at the time of randomization, and pre-operative measurement after randomization and before the surgery. After surgery, patients will be re-randomized to either standard IS or digital IS + text message. Measurements at post-op days 1 and 3 will be taken. The primary objective of this study is to determine the efficacy of incentive spirometry to improve FEV1 in the preoperative setting. The secondary objectives are to determine the efficacy of incentive spirometry to improve FVC and pulse oximetry in the preoperative setting, and FEV1, FVC, and pulse oximetry in the postoperative setting. The exploratory objectives are to determine the daily number of times patients perform incentive spirometry in the postoperative setting and evaluate the rate of pulmonary complications across the 3 preoperative groups.

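### Exploratory complications endpoint: section 9.1 sets the objective across three preoperative arms, but the only group test in section 9.6 is a six-group chi-square

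*Combined protocol and SAP*

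**What the plan says.** **Groups.** The Synopsis objective is "To evaluate the rate of pulmonary complications across the 3 preoperative groups", and section 9.1 repeats it: "evaluate the rate of pulmonary complications across the 3 preoperative groups". The table in section 2.0 has instead "To evaluate the rate of pulmonary complications across all 6 groups".

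**Analysis.** For this endpoint section 9.6 states: "For postoperative complications, Chi-square test will be used to test the differences between six groups". The next sentence is "The univariate logistic regression model will estimate the odds ratio of postoperative complication", with no predictor or contrast named. A stepwise model for a binary outcome may follow; treatment arm is not listed as a term to be kept.

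**Outcome.** All three statements of the objective concern pulmonary complications. The endpoint in section 9.4 is "postoperative complications defined my Modified Accordion Grading System (MAGS"), and the endpoint lists in the Synopsis and section 2.0 agree with it. No grade cut-off is given to make the graded outcome binary.

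**Time.** The endpoint text gives no window. The Schedule of Activities has a row "Assess for AE/Complications" whose last column is postoperative day 3, and section 5.1 evaluates patients to day 3. Section 5.0 adds: "Postoperative outcomes data, including perioperative mortality postoperative complications, length of stay, and need for readmission, will be collected for all patients", with no end date. Section 7.0 has a follow-up form at 1 month, and the Synopsis gives a participant duration of about 1 month.

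**The concern.** Patients are randomised to three arms before surgery and again to two arms on postoperative day 1, which gives 3 x 2 = 6 cells. A six-group test asks whether any cell differs from any other. The question in section 9.1 is narrower: do the three preoperative arms differ? An analyst who follows section 9.6 literally would produce no group test of that question. A significant six-group result could come from either randomisation or from their combination.

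Two reports of this trial could therefore use three or six groups, and pulmonary or all complications, and each could cite the protocol. With no window stated, they could also count events over different periods.

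**Working it through.** **1. The plan's own power figure.** Section 9.5 gives 49 per group, a difference of 0.4 L, SD 0.6, two-sided alpha 0.017. The noncentral t calculation gives 80.62%, so the stated 80.6% reproduces. 49/0.95 rounds up to 52, and 3 x 52 = 156. This covers FEV1 only; nothing is sized for complications.

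**2. Assumed inputs.** The documents give no pulmonary complication rate, only up to 50% for all complications after operations such as pancreaticoduodenectomy and liver resection (section 1.1). All rates and counts below are assumptions. The re-randomisation ratio is not stated; 1:1 is assumed, so 156/6 = 26 per cell and 52 per preoperative arm.

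**3. Power for a preoperative-only effect.** Control 50%, both spirometry arms 30%, alpha 0.05. The noncentrality is λ = Σ nᵢ(pᵢ − p̄)² / [p̄(1 − p̄)], with p̄ = (0.50 + 0.30 + 0.30)/3 = 0.3667.

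- Three arms: λ = 52 × [0.1333² + 2 × 0.0667²] / (0.3667 × 0.6333) = 1.387/0.2322 = 5.97
- Six cells: λ = 26 × [2 × 0.1333² + 4 × 0.0667²] / 0.2322 = 5.97

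The signal is the same, but the critical value rises from 5.99 (2 df) to 11.07 (5 df). Power is 58% for three arms and 43% for six groups. At 147 patients (3 x 49), λ = 5.97 × 147/156 = 5.63, and power is about 56% and 41%.

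| Assumed rates (control vs both spirometry arms), N = 156 | Six-group | Three-arm |
|---|---|---|
| 50% vs 30% | 43% | 58% |
| 30% vs 15% | 35% | 49% |
| 20% vs 10% | 22% | 32% |
| 10% vs 5% | 12% | 17% |

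**4. One data set, two answers.** Suppose 14/26 events in both control cells and 7/26 in the other four, so 56/156 = 0.359 overall.

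- Six groups: 9.33 events expected per cell; X² = [2 × 4.67² + 4 × 2.33²] / (9.33 × 0.641) = 65.33/5.98 = 10.92; 5 df, p = 0.053
- Three arms (28, 14, 14 of 52): 18.67 expected per arm; X² = [9.33² + 2 × 4.67²] / (18.67 × 0.641) = 130.67/11.97 = 10.92; 2 df, p = 0.004

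**5. Attribution.** Two assumed tables, 58 events each, 26 patients per cell (control, standard, digital before surgery; standard/digital after surgery in each pair):

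| Events per cell | Six-group p | Preoperative-arm p | Postoperative-arm p |
|---|---|---|---|
| 15/15, 7/7, 7/7 | 0.015 | 0.0009 | 1.0 |
| 14/6, 13/6, 13/6 | 0.020 | 0.97 | 0.0003 |

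The six-group p-values are similar, although the first table reflects only the preoperative assignment and the second almost wholly the postoperative one.

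**The case against.** **The six-group test matches section 2.0, and any omnibus test leaves the source of a difference open.** Both are true. A reader might infer that the chi-square is invalid or blind to a preoperative effect. It is neither: it answers the section 2.0 objective and keeps 43% power in the case above. The fault is that it does not match section 9.1 and that nothing else in section 9.6 is specified to do so. The logistic model could fill the gap if it named arm as the predictor.

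**The time frames do not contradict each other.** This stands. A reader might set day 3 against 1 month and call it a conflict. However, no section states a window for this endpoint, and the day-3 statement in section 5.1 follows a sentence about the primary endpoint. Day-3 visits, outcomes collected under a division protocol, a 1-month form and a participant duration of about 1 month can be read together. The defect is an omission.

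**The outcome is not drifting from section to section.** This also stands. Every objective says pulmonary, and every endpoint says postoperative complications by MAGS. It is one consistent objective-endpoint mismatch.

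**The worked example is generous.** 14/26 is 54%, above the only rate in the documents. At 13/26 versus 8/26 neither test is significant (p = 0.36 and 0.064). Section 1.1 also reports no significant morbidity differences in the preoperative studies. The example shows that the choice of test can matter, not that it will.

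**A full redesign by randomised factor is not called for.** A reader might infer that separate preoperative and postoperative tests, each at 0.025, are required. No complications objective in the documents compares the postoperative arms alone, and counting only events after re-randomisation needs onset dates that the documents do not show are collected. Such a test is optional.

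**Conclusion.** The point holds and is minor. The Synopsis and section 9.1 disagree with section 2.0 on the groups, and section 9.6 specifies no group test of the section 9.1 objective. The pulmonary-versus-MAGS mismatch, the missing grade cut-off and the missing window are separate wording defects in the same endpoint.

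The main gain from correcting it is a test that answers the stated question. The power difference, about 5 to 15 percentage points in the scenarios tabulated, is secondary. It depends on assumed rates, 1:1 re-randomisation, equal rates in the two preoperative spirometry arms and no postoperative effect. It does not hold everywhere: if only one of the six cells benefits (40% to 15%), simulated power is about 43% for the six-group test against 27% for a pair of factor tests at 0.025 each.

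A reader might infer that the trial's main conclusions are at risk. The documents do not support that: the endpoint is exploratory and the sample size rests on FEV1 alone.

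**What to change.** 1. In section 9.6, add a 2-df chi-square of complications across the three preoperative arms, in all initially randomised patients, as the test of the section 9.1 objective. State how patients who do not have surgery are counted.
2. Name preoperative arm as the predictor in the logistic model, and keep it in any adjusted model rather than leaving it to stepwise selection.
3. Keep the six-group comparison as a supporting or descriptive table, and align section 2.0 with the Synopsis and section 9.1. If the sponsor prefers six groups as the objective, change the Synopsis and section 9.1 instead, and enter preoperative and postoperative arm as separate factors in the logistic model so that an effect can be attributed.
4. Use one outcome throughout: either pulmonary complications, defined, or all postoperative complications by MAGS. Give the grade cut-off that makes it binary.
5. State one time window for the endpoint and reconcile the Schedule of Activities and sections 5.0, 5.1, 7.0 and 9.4 with it.

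A separate postoperative-arm test may be added as exploratory. No alpha split is needed to match the stated objective.

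**Cost.** Items 1 to 3 are wording only, with no change to enrolment or visits. A pulmonary definition may need data fields that the documents do not show. Under the first option in item 3, the trade-off is less sensitivity to an effect confined to one preoperative-by-postoperative combination.

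### The six-group complication test uses groups that exist only after re-randomisation on postoperative day 1, so it counts earlier events and has no cell for patients never re-randomised

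*Combined protocol and SAP*

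**What the plan says.** Section 9.1 describes two randomisations. The first: "The enrolled patients will be randomized 1:1:1 to one of three groups: control, standard IS, and digital IS + text message". The second: "After surgery, patients will be re-randomized to either standard IS or digital IS + text message". Section 5.0 and the schedule of activities time the second: "On postoperative day 1, patients will be re-randomized".

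The complication objective appears in two forms. The synopsis and section 9.1 set out to "evaluate the rate of pulmonary complications across the 3 preoperative groups". The table in section 2.0 reads "To evaluate the rate of pulmonary complications across all 6 groups". Section 9.6 follows the second form: "For postoperative complications, Chi-square test will be used to test the differences between six groups". The logistic regression that comes after it in 9.6 names no treatment term.

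The schedule of activities marks assessment of adverse events and complications at every visit, including the day of surgery. Section 5.0 says postoperative outcomes "will be collected for all patients as per protocol for the Division of Hepatobiliary Surgery". Section 9.6 opens with "The analysis will be intent-to-treat approach" but does not say to which of the two randomisations this applies. The evaluability rule in section 5.1 covers the primary endpoint only.

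**The concern.** Each randomisation supports a comparison that starts when it is made. A six-group label is complete only on postoperative day 1, and this creates two problems.

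- **Postoperative arms.** A complication on the day of surgery, or on day 1 before the second assignment, cannot be caused by the postoperative device. Nothing in the plan removes it from the count, so it adds the same expected number of events to both postoperative arms and blurs any difference between them.
- **Preoperative arms.** A patient who dies, withdraws or for any other reason is not re-randomised still belongs to a preoperative arm and still has outcome data, but has no place in a six-group table. Leaving such patients out selects on something that happens after the first randomisation. If early complications make re-randomisation less likely, and preoperative spirometry affects early complications, the comparison of the preoperative arms is distorted.

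The stake is the interpretation of an exploratory endpoint.

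**Working it through.** **The plan's own figure.** The documents give no power for the complication test. The only power statement is for FEV1 (section 9.5): 49 per group, difference 0.4 L, SD 0.6, two-sided level 0.017. A noncentral t calculation gives 80.6%, as stated. Enrolment is 49/0.95 = 51.6, rounded up to 52 per group, and 3 × 52 = 156. Both reproduce.

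**Cell size.** 3 × 2 = 6 groups. With equal allocation at the second randomisation (the ratio is not stated), 156/6 = 26 per cell.

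**Power formula.** For k groups of sizes n_i and risks p_i, with overall risk p̄, the noncentrality is λ = Σ n_i(p_i − p̄)² / [p̄(1 − p̄)] on k − 1 degrees of freedom. The level is 5% two-sided (section 9.6).

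**1. Early events and the postoperative part of the six-group test.** Assume later-complication risks of 45% and 27% in the two postoperative arms and no preoperative effect. Let e be the share of patients who already have a complication at re-randomisation. The any-complication risk is e + (1 − e)p.

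| e | risks | difference | risk ratio | λ | power, 5 df |
|---|---|---|---|---|---|
| 0 | 45.0% v 27.0% | 18.0 points | 0.60 | 5.48 | 40% |
| 5% | 47.8% v 30.7% | 17.1 points | 0.64 | 4.78 | 35% |
| 10% | 50.5% v 34.3% | 16.2 points | 0.68 | 4.19 | 31% |
| 20% | 56.0% v 41.6% | 14.4 points | 0.74 | 3.24 | 24% |

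First row: λ = 156 × 0.09² / (0.36 × 0.64) = 5.48.

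This is dilution only. In 20,000 simulated trials with no postoperative effect and 20% early events, a comparison of 78 v 78 rejected in 5.3%, close to the nominal 5%.

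**2. Six groups against three for the preoperative objective.** Assume 50% in control, 30% in both spirometry arms, and no postoperative effect. λ = 5.97 either way. On 2 df (3 × 52) power is about 58%; on 5 df (6 × 26) it is about 43%. The loss comes from the three extra degrees of freedom.

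**3. Patients never re-randomised.** Assume early complications in 20% of control and 10% of a spirometry arm, and a later risk of 30% in both. With everyone counted, the risks are 0.20 + 0.80 × 0.30 = 44% and 0.10 + 0.90 × 0.30 = 37%, a difference of 7.0 points. If a share f of those with an early complication e is not re-randomised and is dropped, the observed risk is [e(1 − f) + (1 − e) × 0.30] / (1 − ef):

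| f | observed risks | difference | lost of 52 per arm |
|---|---|---|---|
| 25% | 41.1% v 35.4% | 5.7 points | 2.6 v 1.3 |
| 50% | 37.8% v 33.7% | 4.1 points | 5.2 v 2.6 |
| 100% | 30.0% v 30.0% | 0.0 points | 10.4 v 5.2 |

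If few patients are lost, little changes. Take 50% v 30% and suppose every lost patient had an event. Losing 2% from each arm gives (0.48/0.98) − (0.28/0.98) = 20.4 points instead of 20.0. Losing 2% v 1% gives (0.48/0.98) − (0.29/0.99) = 19.7 points.

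**The case against.** **Reconciling the group count would remove most of this.** The synopsis and section 9.1 already state the objective across three preoperative groups. If 9.6 followed them, nobody would need a six-group label and no postoperative contrast would remain to dilute. This largely stands, and it narrows the point. It does not remove it, because sections 2.0 and 9.6 as written use six groups, and 9.6 is the text an analyst would follow.

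**Two premises are inferred.** No passage says that patients without a second assignment are excluded, and no passage defines the complication window. That is correct. A reader might infer that the plan deliberately drops these patients or expressly counts from surgery; the documents say neither. They name a test with no cell for these patients, give no rule for placing them, and mark complication assessment on the day of surgery.

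**Stronger readings that the documents do not support.**
- That early events invalidate the postoperative comparison. They precede the second randomisation, so they are balanced in expectation and the type I error holds.
- That the preoperative arms have no other test. FEV1, FVC and oximetry have a three-group comparison in 9.6. The gap concerns complications only, and the logistic regression could carry a preoperative term, although none is named.
- That the loss should be read from a 78 v 78 digital-versus-standard test. On the same 45% v 27% assumption such a test falls from 65% to 44% power at 20% early events, but the plan contains no such test for complications.
- That the early events lost are the ones preoperative spirometry is meant to prevent. Section 1.1 gives its aim as preventing pulmonary complications, and nothing describes the early events as pulmonary.

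**Conclusion.** The point holds in a limited form. Followed as written, the six-group test counts complications that precede the second assignment and has no place for a patient who never receives it. The stated objective in the synopsis and 9.1 concerns the three preoperative arms, and the analysis is meant to be intent-to-treat.

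For the postoperative part, the cost is power: about 40% falling to about 24% if 20% of patients have an early event, under the 45% v 27% assumption. For the preoperative part, spreading the comparison over six cells costs about 15 percentage points of power (58% to 43%) at 50% v 30%. The distortion from losing patients ranges from negligible at about 2% lost to substantial only if a large share of those with early complications miss re-randomisation. All complication risks, early-event rates and loss rates here are assumptions, because the documents supply none for this purpose. The endpoint is exploratory, so this is a minor, inexpensive correction.

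**What to change.** In section 9.6, replace the six-group test with a comparison of complications across the three preoperative arms as first randomised. Count from surgery and include every patient who had surgery, whether or not re-randomised.

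If digital versus standard spirometry after surgery is also to be compared on complications, state it as a separate analysis by second assignment. Count only complications with onset after re-randomisation, and report earlier ones as a baseline characteristic.

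Reconcile the complication objective in the synopsis, section 2.0 and section 9.1 with the revised 9.6.

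The cost is wording, plus recording the onset of each complication relative to re-randomisation, which needs enough precision to separate events before and after assignment on day 1. No patients or procedures are added.
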